3.2 Exclusion Criteria

Prospective participants who meet any of the following criteria will not be eligible to participate in the study:

Prior Therapy/ Procedures

- 1. Post-ASCT anti-lymphoma or investigational therapy. Immediate post-ASCT consolidative radiation therapy is allowed as long as it occurs prior to initiation of study therapy. Baseline imaging and PFTs must be performed after completion of radiation.
- 2. Previous allogeneic transplant
- 3. Total BCNU dose of > 600 mg/m² with prior treatments including transplant conditioning regimen
- 4. Live vaccine within 30 days prior to Day 1 of protocol therapy (e.g. measles, mumps, rubella, varicella, yellow fever, rabies, BCG, oral polio vaccine, and oral typhoid)

Other Illnesses and Conditions

- 5. Refractory to prior brentuximab vedotin (i.e. progression while on treatment)
- 6. Refractory to prior anti-PD-1/PD-L1 agent
- 7. History of prior ≥ Grade 3 hypersensitivity to either brentuximab vedotin or nivolumab
- 8. History of another primary malignancy that has not been in remission for at least 3 years. Exceptions include:
 - Basal cell carcinoma of the skin or
 - Squamous cell carcinoma of the skin that has undergone potentially curative therapy or
 - In situ cervical cancer.
- 9. Known active central nervous system (CNS) involvement by lymphoma, including parenchymal and/or lymphomatous meningitis.
- 10. History of progressive multifocal leukoencephalopathy (PML)
- 11. Grade ≥ 2 peripheral neuropathy at the present time
- 12. Prior diagnosis of inherited or acquired immunodeficiency
- 13. Condition requiring systemic treatment with either corticosteroids (> 10 mg daily prednisone or equivalent) or other immunosuppressive medications within 14 days of study drug administration. Exceptions are:
 - Inhaled or topical steroids and
 - Adrenal replacement doses > 10 mg daily prednisone equivalents in the absence of active autoimmune disease.

Participant MRN (COH Only):	Participant Initials (F, M, L):
Institution:	

- ___ 14. Uncontrolled illness including ongoing or active infection
- ___ 15. History of or active pneumonitis or interstitial lung disease:
 - For history of pneumonitis to be an exclusion, patient had to have required supplemental oxygen or corticosteroid treatment. Radiographic changes alone are not an exclusion.
- ___ 16. An active, known or suspected autoimmune disease. The following are exceptions:
 - Vitiligo,
 - Hemolytic anemia associated with the lymphoma (history of or at the present time)
 - Type I diabetes mellitus,
 - Residual hypothyroidism due to autoimmune condition only requiring hormone replacement,
 - Psoriasis not requiring systemic treatment, or
 - Conditions not expected to recur in the absence of an external trigger
- ___ 17. Active or known history (standard pre-ASCT assessments) of:
 - Hepatitis B or C infection
 - Human immunodeficiency virus (HIV)
 - Acquired immunodeficiency syndrome (AIDS)
- ___ 18. Women who are pregnant or lactating
- ___ 19. History of a cerebral vascular event (stroke or transient ischemic attack), unstable angina, myocardial infarction, or cardiac symptoms consistent with New York Heart Association Class III-IV within 6 months prior to Day 1 of protocol therapy
- ___ 20. History or current evidence of any condition, therapy, or laboratory abnormality that might confound the results of the trial, interfere with the subject's participation for the full duration of the trial, or is not in the best interest of the subject to participate, in the opinion of the treating investigator

Noncompliance

- ___ 21. Prospective participants who, in the opinion of the investigator, may not be able to comply with all study procedures (including compliance issues related to feasibility/logistics).

Eligibility Confirmed* by (Choose as applicable):	Print Name	Signature	Date
 Site PI			
 Authorized study MD			
 Study Nurse			
 Study CRA/ CRC			
 Other: _____			

*Eligibility should be confirmed per institutional policies.

4.0 PARTICIPANT ENROLLMENT

NOTE: Sites must meet activation requirements prior to enrolling participants.

4.1 Pre-Enrollment Informed Consent and Screening Procedures

Diagnostic or laboratory studies performed exclusively to determine eligibility will be done only after obtaining written informed consent. Studies or procedures that are performed for clinical indications (not exclusively to determine study eligibility) may be used for baseline values and/or to determine pre-eligibility, even if the studies were done before informed consent was obtained. The informed consent process is to be fully documented (see [Section 16.4](#)), and the prospective participant must receive a copy of the signed informed consent document.

Screening can initiate **21 days after ASCT** and screening assessments are listed in [Section 10.0](#).

Participants who signed informed consent prior to ASCT must have completed ASCT and have recovered from ASCT toxicities to be eligible per [Section 3.0](#) to receive protocol therapy.

4.2.2 Slot verification and reservation

Designated study staff should call the DCC to verify current slot availability, and to reserve a slot for a specific prospective subject.

The DCC should be notified of cancellations of prospective participants holding slots as soon as possible.

4.2.3 Registration Process

To register a participant, the subsequent procedure is to be followed.

1. The participating site's data manager/coordinator/research nurse should contact the DCC via telephone or email to provide notification regarding the pending registration and communicate desired timeline of the registration, especially if it must be completed promptly to meet the registration window.
2. The data manager/coordinator/research nurse should then e-mail copies to [contact] of the following documents to the DCC:
 - Registration Cover Sheet ([Appendix B](#))
 - Completed Eligibility Criteria List (printed from [Section 3.0](#) of the protocol)
 - Source documentation to support eligibility criteria**
 - Signed informed consent document
 - Signed HIPAA authorization form (if separate from the informed consent document)
 - Signed subject's Bill of Rights (COH only)

**For COH participants, provide copies of source documentation only if not readily available as a finalized record in the COH Electronic Medical Record (EMR).

3. After having received all transferred documentation, the DCC will complete the review the documents to verify eligibility, working with the participating site as needed to resolve any missing required source elements. A participant failing to meet all protocol eligibility requirements will not be registered.
4. Once eligibility has been confirmed, DCC staff will register the participant by: assigning a subject accession number, register the subject on study centrally into a COH clinical trials management system for non-COH participants, and enter the subject into the eCRF system, Medidata RAVE.
5. Once registration has been completed, DCC staff will send a Confirmation of Registration Form, including the participant study number to:
 - the site study team: Site Lead Investigator, treating physician, protocol nurse, CRC and pharmacy
 - the COH sponsor team designees

4.3 Screen Failures and Registered Participants Who Do Not begin Study Treatment

The DCC is to be notified of all participants who sign consent but do not meet eligibility criteria or do not initiate protocol therapy. For non-COH sites, the reason for screen failure will be documented in registration coversheet (see [Appendix B](#)) and submitted to the DCC.

5.0 TREATMENT PROGRAM

5.1 Treatment Program Overview

This is a multi-center, open-label, Phase 2 clinical trial for participants with relapsed or refractory Hodgkin lymphoma who have undergone autologous stem cell transplant (ASCT). Participants will initiate protocol therapy within 30 to 60 days post stem cell reinfusion. Study PI can grant exception for a patient to start as late as 75 days post stem cell reinfusion with a reasonable justification for delay (e.g. recovery from post-ASCT toxicity) and this will not be a protocol deviation, nor require an exception to be filed. Nivolumab and brentuximab vedotin will be administered in an outpatient setting in each 21-day cycle.

Participants will receive up to 8 cycles of protocol therapy. If one agent is discontinued due to toxicity, then the participant may continue to receive single agent monotherapy.

Participants who complete protocol therapy ([Section 5.6](#)) will undergo follow-up ([Section 5.7](#)). Windows for all assessments and treatments are detailed in [Section 10.0](#).

5.2 Treatment Cycle Definition

In the absence of treatment-related delay, a cycle of therapy is defined as 21 days with a \pm 3 day window.

Day 1 of a cycle is defined as the administration of brentuximab vedotin ([Section 5.3](#)); the only exception to this will be if brentuximab vedotin is held or discontinued in which case Day 1 of a cycle will be defined as the administration of nivolumab.

5.3 Treatment Plan

[Table 5.3](#) describes the combination regimen. The starting dose for brentuximab vedotin will be 1.8 mg/kg. Protocol therapy must be initiated within 30 to 60 days post stem cell reinfusion. Study PI can

grant exception for a patient to start as late as 75 days post stem cell reinfusion with a reasonable justification for delay (e.g. recovery from post-ASCT toxicity) and this will not be a protocol deviation, nor require an exception to be filed.

Table 5.3 Dosing regimen and schedule

Agent	Dose	Route	Schedule	Max. Cycles
Brentuximab Vedotin	1.8 mg/kg	IV over 30 minutes	Day 1 of each 21-day cycle	8
Nivolumab	3 mg/kg	IV over 60 minutes	Day 1 of each 21-day cycle	

5.4 Agent Administration

Mandatory prophylaxis for infusion related reaction must be initiated **at least 30 minutes** prior to agent administration.

- For participants **without** history of infusion reaction to brentuximab vedotin or nivolumab. Recommended pre-medication to include, per institutional standard:
 - Acetaminophen/paracetamol
 - Anti-histamine (e.g. diphenhydramine)
- For participants **who have experienced** an infusion related reaction to brentuximab vedotin or nivolumab (prior to this study, or on this study while not taking corticosteroid prophylaxis). Recommended pre-medication to include (and modifiable per institutional standard):
 - Acetaminophen/paracetamol 325 to 1000 mg
 - Anti-histamine: Diphenhydramine 25–50 mg (or equivalent)
 - Corticosteroid: Hydrocortisone IV no more than 100 mg (or equivalent)
 - Ranitidine may be considered
- For participants **who experience** infusion related reaction to study agents **while taking prophylactic corticosteroids**.
 - Premedication to follow above, but increase corticosteroids:
 - Methylprednisolone 40 mg IV (or equivalent e.g. hydrocortisone IV 200 mg).

For supportive care during infusion reaction, see [Section 5.9.2](#).

5.4.1 Brentuximab Vedotin

Brentuximab vedotin will be administered as a 30 minute IV infusion on Day 1.

When both agents are administered sequentially, brentuximab vedotin will be administered first. The infusion must have ended at least 30 minutes prior to the nivolumab infusion.

Dosing is based on participant actual body weight. It is not necessary to re-calculate subsequent doses if the participant weight is within 10% of the weight from baseline. Other dose adjustments for changes in body weight are permitted per institutional standard. An exception to weight-based dosing is made for participants weighing > 100 kg; doses will be based on 100 kg for these individuals. Rounding is permissible within 5% of the nominal dose.

Management and dose reductions associated with brentuximab vedotin AEs are outlined in [Section 6.2](#).

5.4.2 Nivolumab

Nivolumab will be administered as a 60 minute (\pm 5 minute) IV infusion on Day 1.

Nivolumab should be administered at least 30 minutes after completing treatment with brentuximab vedotin on Day 1.

The nivolumab dose is fixed at 3 mg/kg. Doses of nivolumab may be interrupted, delayed, or discontinued depending on how well the participant tolerates the treatment. Refer to [Section 8.1.9](#) for additional administration information.

The dosing calculations for nivolumab should be based on the actual body weight at baseline. If the subject's weight on the day of dosing differs by $>$ 10% from the weight used to calculate the original dose, the dose must be recalculated. All doses should be rounded to the nearest milligram. There will be no dose modifications allowed.

Management and dose delays associated with nivolumab AEs are outlined in [Section 6.2](#).

5.5 Assessments and Special Monitoring

Refer to [Section 10.0](#) for schedule of assessments. **Note:** on days when agent(s) is/are administered, assessments are to be completed (and results reviewed if a safety or response assessment) prior to administration of agent(s).

5.5.1 Special Monitoring

- *Infusion reactions*
 - Infusion or hypersensitivity reactions may occur to either brentuximab vedotin or nivolumab.
 - Since nivolumab contains only human immunoglobulin protein sequences, it is unlikely to be immunogenic and induce infusion or hypersensitivity reactions.
 - If such a reaction were to occur, it might manifest with fever, chills, rigors, headache, rash, pruritus, arthralgias, hypotension, hypertension, bronchospasm, or other allergic-like reactions.
 - Refer to [Section 5.9.2](#) for management guidelines.
- *Immune-related Adverse Events (AEs)*
 - Nivolumab is associated with AEs that can differ in severity and duration than AEs caused by other therapeutic classes.
 - Early recognition and management of AEs associated with nivolumab may mitigate severe toxicity.
 - Refer to [Section 5.9.2](#) for management guidelines.

5.6 Duration of Therapy and Criteria for Removal from Study Treatment

Participants will receive protocol therapy until one of the below criteria are met:

- Disease progression
 - **Note:** Following consultation with the Study PI, participants who meet progression per 2014 Lugano classification [53] but who meet the criteria of "indeterminate response" (IR) according to the provisional modification to the 2014 Lugano Classification, the LYRIC

criteria [1] ([Appendix H](#)), and are deriving clinical benefit may continue to receive protocol therapy beyond progression as long as they meet the following criteria:

- Continue to meet treatment criteria
- Investigator-assessed clinical benefit and subject is tolerating study drug.
- Tolerance of study drug
- Stable performance status
- Treatment beyond progression will not delay an imminent intervention to prevent serious complications of disease progression (e.g., CNS metastases)
- *If the patient has IR per LYRIC criteria and is receiving therapy beyond progression:*
 - A confirmatory PET-CT should be performed within 12 weeks after initial progression to determine whether the patient meets PD criteria according to the LYRIC criteria [1].
 - Further progression is defined according to the LYRIC criteria
 - Protocol therapy should be discontinued permanently upon documentation of PD per the LYRIC criteria
- Participant receives 8 cycles (~ 6 months) of protocol therapy
- Unacceptable toxicity related to protocol therapy despite dose delay/ modification
 - **Note:** If one agent is delayed due to toxicity, then participants may continue with monotherapy for the other agent.
- General or specific changes in the participant's condition (including intercurrent illness) which render the participant unacceptable for further treatment in the judgment of the investigator
- Withdrawal of consent for further protocol therapy by the participant (See [Section 16.5](#))

Once participants meet criteria for removal from protocol therapy, the participant should then proceed to Follow-up.

Documentation of the reason for discontinuing protocol therapy and the date effective should be made in the medical record and appropriate eCRF. The COH DCC and the Study PI should be promptly notified of the change in participant status.

5.7 Follow-Up

Following completion of protocol therapy, participant will enter follow-up. Note, the safety follow-up visits may occur concurrently with other follow-up visits:

- **Safety Follow-up** - All participants will undergo safety follow-up visits, typically at 30 days and 100 days following the end of treatment.
- **Active Response Follow-Up** – for participants who have yet to progress/relapse. These visits also involves the collection of research samples. This period has a maximum of 18 months from start of treatment.
- **Long Term Follow-Up** – for all participants who have progressed/relapsed OR completed Active Response Follow-Up. This follow-up will be performed typically via medical record review. It will entail (a) Disease status (for those who have yet to relapse/progress) (b) Vital status (all participants). The long-term follow-up period will have a maximum duration of 5 years (from start of treatment).

See [Section 10.0](#) for details and windows.

5.8 Duration of Participation and Criteria for End of Participation

Study participation may conclude when any of the following occur:

- Completion of study activities (treatment and follow-up)
- Participant withdrawal (see [Section 16.5](#)).
- Participant is lost to follow-up. All attempts to contact the participant must be documented.
- At the discretion of the investigator for reasons including but not limited to study termination, behavioral or administrative reasons

Documentation of the reason for discontinuing study participation and the date effective should be made in the medical record and appropriate eCRF. The COH DCC should be promptly notified of the change in participant status.

5.9 Supportive care, Prohibited and Concomitant Medications/ Therapies

Participants must be instructed not to take any additional medications (including over-the-counter products) during the trial without prior consultation with the investigator.

5.9.1 *Prohibited medications/ therapies*

The following medications/ therapies are **prohibited** from Day 1 of protocol therapy until end of protocol therapy (last day of study agent or decision to end study agent(s) whichever occurs later):

- Co-medication that may interfere with study results; e.g. immuno-suppressive agents other than corticosteroids used for treatment of an IrAE are prohibited during the treatment period, unless discussed with the Study PI and felt to be of low clinical risk to the participant.
- Live attenuated vaccines
- Herbal and natural remedies

The following medications/therapies are prohibited any time after ASCT, active protocol treatment, or follow-up. If the patient receives one of these therapies in the absence of disease progression, the patient will be censored at the time of initiation.

- Other investigational therapy
- Concurrent anti-cancer therapy: chemotherapy, biological response modifiers, hormone therapy, surgery, palliative radiation therapy, or immunotherapy).

5.9.2 *Supportive care and permitted medications/ therapies*

With the exception of prohibited therapies (see [Section 5.9.1](#)), participants should receive prophylactic or supportive care as clinically indicated per institutional policies and suspected immune-related AEs (irAE) guidelines stated below.

Blood products

- *Platelet and/or red blood cell supportive growth factors or transfusions*
 - Permitted when applicable
- *Colony stimulating factors (CSFs)*
 - Permitted for treatment of neutropenia per institutional practice.

Corticosteroids

- *Topical, ocular, intra-articular, intranasal, and inhalational corticosteroids (with minimal systemic absorption)*
 - Permitted
- *Systemic corticosteroids*
 - Physiologic replacement doses permitted even if > 10 mg/day prednisone or equivalent.
- *Brief course of corticosteroids (< 3 weeks)*
 - Permitted for prophylaxis (e.g. contrast dye allergy)
 - Permitted for treatment of non-autoimmune conditions (e.g. delayed-type hypersensitivity reaction caused by contact allergen)

Strong CYP3A4/5 inhibitors

Closely monitor for AEs when administered concomitantly with brentuximab vedotin.

Required prophylaxis

Standard international guidelines for infection prophylaxis for herpes simplex virus (HSV), varicella-zoster virus (VZV), and Pneumocystis jiroveci (PCP) after ASCT must be followed. Per international guidelines, Herpes virus prophylaxis with acyclovir or similar agent and pneumocystis jiroveci (PCP) prophylaxis is required for all patients on this study. Administer prophylaxis from the time of engraftment (or the time of first study treatment dosing) for at least 9 months after ASCT. If herpes virus or PCP prophylaxis is held, the reasoning (e.g. renal dysfunction) must be documented.

- *First Choice*
 - Trimethoprim-sulfamethoxazole: 1 double-strength (DS) tablet (160/800 mg) orally 3 times/week; 1 DS tablet orally daily; 1 single-strength (80/400 mg) tablet orally daily; or 1 DS tablet two times a day 2 days a week.
- *First Alternative*
 - Atovaquone: 750 mg twice daily or 1500 mg once daily, orally
- *Other Alternatives*
 - Dapsone: 50 mg orally 2 times/day; or 100 mg orally daily
 - Pentamidine: 300 mg every 3-4 weeks by Respigard II™ nebulizer

Management of infusion reactions

Treatment recommendations are provided below may be modified based on local treatment standards and guidelines as appropriate.

Grade 2 infusion reactions

- If the onset of a reaction occurs during an infusion,
 - The infusion may be interrupted for treatment of the infusion-related reaction, and/or
 - The infusion time may be extended.
 - Recommended treatments include: antihistamines, corticosteroids, and/or bronchodilator therapy, as appropriate.

Grade 3 or 4 infusion reactions

- If the onset of a reaction occurs during infusion, the infusion must be interrupted.
- Begin an IV infusion of normal saline
- Recommend treatments include:
 - bronchodilators,
 - epinephrine 0.2 to 1 mg of a 1:1,000 solution for subcutaneous administration or 0.1 to 0.25 mg of a 1:10,000 solution injected slowly for IV administration, and/or
 - Diphenhydramine 50 mg IV with methylprednisolone 100 mg IV (or equivalent), as needed.
- Monitor until the investigator is comfortable that the symptoms will not recur.
- Follow institutional guidelines for anaphylaxis.
- For late-occurring hypersensitivity symptoms (e.g. appearance of a localized or generalized pruritus within 7 days post-treatment):
 - Symptomatic treatment may be given (e.g., oral antihistamine, or corticosteroids)

Management of immune-related AEs

The following immune-related AEs (irAEs) related to nivolumab should be managed as outlined below.

5.9.2.1 Hepatic

- Rule out non-inflammatory causes. If non-inflammatory cause, treat accordingly and continue I-O therapy. Consider imaging for obstruction.
- Patients on IV steroids may be switched to an equivalent dose of oral corticosteroids (e.g. prednisone) at start of tapering or earlier, once sustained clinical improvement is observed. Lower bioavailability of oral corticosteroids should be taken into account when switching to the equivalent dose of oral corticosteroids.

For patients with baseline LFT that are within normal limits:***Grade 1: AST or ALT > ULN – 3.0 x ULN and/or Total bilirubin > ULN -1.5X ULN***

- Continue liver function tests (LFT) monitoring per protocol
- If worsens treat as Grade 2 or 3-4

Grade 2: AST or ALT > 3.0 to ≤ 5 x ULN and/or Total bilirubin >1.5 to ≤ 3 x ULN

- Increase frequency of monitoring to every 3 days
- If returns to baseline: Resume routine monitoring, resume therapy per protocol
- If elevations persist > 5-7 days or worsen :
 - 0.5-1 mg/kg/day methylprednisolone or oral equivalent and when LFT returns to grade 1 or baseline, taper steroids over at least 1 month, consider prophylactic antibiotics for opportunistic infections and resume nivolumab per protocol

Grade 3-4: AST or ALT > 5 x ULN and /or Total bilirubin >3 x ULN

- Increase frequency of monitoring to every 1-2 days
- Administer 1.0 to 2.0 mg/kg/day methylprednisolone IV or IV equivalent. The recommended starting dose for grade 4 hepatitis is 2 mg/kg/day methylprednisolone IV.

- Add prophylactic antibiotics for opportunistic infections
- Consult gastroenterologist
- If returns to grade 2:
 - Taper steroids over at least 1 month
- If does not improve in >3-5 days, worsens or rebounds:
 - Add mycophenolate mofetil 1 gram (g) twice daily (BID)
 - If no response within an additional 3-5 days, consider other immunosuppressants

For patients with baseline LFTs (transaminases or bilirubin) in the Grade 1 range (AST or

ALT > ULN to 3.0 x ULN and/or total bilirubin > ULN to 1.5 x ULN) should be managed according to the hepatic algorithm as applied to the absolute increase in AE grade level above baseline. Therefore, for these patients, management of a Grade 3 LFT abnormality would be per the Grade 2 algorithm, and management of a Grade 4 LFT abnormality would be per the Grade 3 algorithm.

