Organ Function Criteria and Pregnancy11. ANC \geq 1000/mm³12. Platelets \geq 50,000/mm³13. Hemoglobin \geq 8 g/dL14. Total bilirubin \leq 1.5 x ULN OR 3 x ULN for Gilbert's disease15. AST and ALT \leq 2.5 x ULN16. Creatinine clearance* \geq 40 mL/min per 24 hour urine collection or the Cockcroft-Gault formula

* Calculated per institutional standard

$$\text{CrCl} \text{ (mL/min)} = \frac{(140\text{-age}) \times \text{actual body weight (kg)}}{72 \times \text{serum creatinine (mg/dL)}} \text{ (x 0.85 for females)}$$

Or

$$\text{CrCl} \text{ (mL/min)} = \frac{(140\text{-age}) \times \text{actual body weight (kg)}}{0.8136 \times \text{serum creatinine (umol/L)}} \text{ (x 0.85 for females)}$$

17. Forced expiratory volume in one second (FEV1) and carbon monoxide diffusion capacity (DLCO) (adjusted for Hb) \geq 50% adjusted18. WOCBP only: Negative urine or serum pregnancy test (minimum sensitivity 25 IU/L or equivalent units of HCG)

- If the urine test is positive or cannot be confirmed as negative, a serum pregnancy test will be required

ANC:	Date:
Plts:	Date:
Hgb:	Date:
ULN:	Date:
Bil:	
ULN: ALT:	Date:
ULN: AST:	Date:
ULN:	Date:
Serum Cr:	
Cr Cl:	

FEV1:	Date:
DLCO:	
Urine test:	Date:
Serum test:	

Contraception

19. Woman of childbearing potential (WOCBP): use two effective methods of contraception (hormonal or barrier method) or be surgically sterile, or abstain from heterosexual activity for the course of the study through 7 months post last dose of nivolumab.

- WOCBP defined as not being surgically sterilized or have not been free from menses for > 1 year.

Male: use two effective methods of contraception (barrier method) or abstain from heterosexual activity with the first dose of study therapy through 7 months post last dose of nivolumab.

Participant MRN (COH Only):

Participant Initials (F, M, L):

Institution:

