6.2 Dose Modification/Delays

- Toxicities will be graded using the NCI [CTCAE v 4.0](#).
- Baseline values are from the last values obtained prior to treatment.
- If one agent is held due to toxicity for a given cycle, administration of the delayed agent should resume once the toxicity is resolved on the same schedule with the next cycle of combination therapy.
- If one agent is permanently discontinued, then the participant may continue monotherapy with the other agent.
- If both agents are held together and the toxicity lasts > 6 weeks, then protocol therapy will be discontinued.
- **Nivolumab dose management guidelines** are described in [Table 6.2.1](#).
 - Management algorithms for nivolumab have been developed to assist investigators in assessing and managing the following groups of AEs: Gastrointestinal, Renal, Pulmonary, Hepatic, Endocrinopathies, Skin, and Neurological. The algorithms have been incorporated into [Table 6.2.1](#) and can also be found in the Nivolumab IB. The guidance provided in these algorithms should not replace the Investigator's medical judgment but should complement it.
 - Dose reductions or dose escalations are not permitted for nivolumab.
 - Asterisk (*) in [Table 6.2.1](#): Following consultation with the Study PI, treatment delay > 6 weeks due to prolonged steroid taper is permissible.
 - Dosing interruptions or delays lasting > 6 weeks that occur for non-nivolumab-related reasons may be allowed if approved by the Study PI. Prior to re-initiating treatment in a participant with a dosing interruption lasting > 6 weeks, the Study PI must be consulted.

- **Brentuximab vedotin dose modification/ delay** are described in [Table 6.2.2](#).
 - Doses reduced for brentuximab vedotin-related toxicity should not be re-escalated without discussion with the Study PI.

Table 6.2.1 Dose management guidelines for Nivolumab

Toxicity	Nivolumab Dose Management Guidelines
Hematological Toxicity	
Anemia or thrombocytopenia Grade 3 Platelets: < 50,000 - 25,000/mm³	Continue nivolumab
Anemia or thrombocytopenia Grade 4 Platelets <25,000/mm³	
 • Hold nivolumab • Once toxicity resolves \leq Grade 2 resume nivolumab per protocol • Permanently discontinue if there is a treatment delay $>$ 6 weeks.
Neutropenia Grade 3 ANC <1000 - 500/mm³	
 • Continue nivolumab • Consider growth factor (G-CSF) support

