Concurrent ≥ Grade 2 AST or ALT (> 3 x ULN) AND total bilirubin > 2 x ULN	
 Discontinue nivolumab therapy See Section 5.9.2.1 for supportive care.
Hepatic (AST, ALT, Total bilirubin) – when baseline LFTs are Grade 1	
Note: for participants with baseline LFTs that are within normal limits , hepatic dose management guidelines above should be followed.	
Grade 1 and 2 G1: AST or ALT > ULN- 3.0 xULN and/or Total bilirubin > ULN -1.5 x ULN G2: AST or ALT > 3.0 to ≤ 5 x ULN OR T. bili > 1.5 to ≤ 3 x ULN	
 Continue nivolumab per protocol See Section 5.9.2.1 for supportive care.
Low Grade 3 AST or ALT > 5-≤ 8 x ULN x ULN OR total bilirubin >3-≤ 5 x ULN	
 Hold the dose of nivolumab See Section 5.9.2.1 for supportive care. If toxicity resolves within 5 days to baseline resume nivolumab per protocol If elevations persist > 5-7 days or worsen 
 Resume therapy per protocol when LFT returns to Grade ≤ 2 or baseline and when steroid taper (≥ 1 month*) is complete. (* See exception in Section 6.2.) Discontinue treatment if toxicity lasts for > 6 weeks or unable to initiate steroid taper within a 6 week period.

Toxicity	Nivolumab Dose Management Guidelines
High Grade 3 and Grade 4 AST or ALT > 8 x ULN OR total bilirubin >5 x ULN	
 Discontinue nivolumab therapy See Section 5.9.2.1 for supportive care.
Concurrent \geq Grade 2 AST or ALT ($> 3 \times \text{ULN}$) AND total bilirubin $> 2 \times \text{ULN}$	
 Discontinue nivolumab therapy See Section 5.9.2.1 for supportive care.
Renal (Creatinine)	
Grade 1 Creatinine > ULN and > than baseline but $\leq 1.5 \times \text{baseline}$	
 Continue nivolumab per protocol See Section 5.9.2.2 for supportive care. If worsens: 
 Treat as Grade 2 or 3/4

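### For patients with Grade 1 baseline liver tests, Section 5.9.2.1 and Table 6.2.1 give opposite nivolumab instructions in the High Grade 3 band: resume in one, discontinue in the other.

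*Combined protocol and SAP*

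**What the plan says.** Section 5.9.2.1 sets out a hepatic algorithm by grade. Its top tier is undivided: "Grade 3-4: AST or ALT > 5 x ULN and /or Total bilirubin >3 x ULN". Patients whose transaminases or bilirubin are already Grade 1 at baseline "should be managed according to the hepatic algorithm as applied to the absolute increase in AE grade level above baseline". The section then gives the consequence: "management of a Grade 3 LFT abnormality would be per the Grade 2 algorithm", and a Grade 4 abnormality follows the Grade 3 algorithm.

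The Grade 2 algorithm has two exits. If values return to baseline, therapy resumes. If elevations persist beyond 5-7 days or worsen, steroids are given, and once liver tests are back to Grade 1 or baseline the instruction is to "taper steroids over at least 1 month, consider prophylactic antibiotics for opportunistic infections and resume nivolumab per protocol".

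Table 6.2.1 in Section 6.2 has a separate hepatic block for Grade 1 baselines, and it splits Grade 3. Low Grade 3 is hold, then resume on recovery. The row for High Grade 3 and Grade 4, "AST or ALT > 8 x ULN OR total bilirubin >5 x ULN", says to discontinue nivolumab and refers to Section 5.9.2.1 for supportive care.

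**The concern.** The two texts address the same patients and the same decision. One carries every Grade 3 value to resumption, and the other stops nivolumab in the upper part of Grade 3. The discontinue row also sends the reader back to the section that says resume, so following the cross-reference does not settle the matter.

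The study runs at six sites. Two of them could see the same liver value, each follow a written instruction, and one stop nivolumab while the other re-exposes the patient. That is a participant-safety matter first. Safety and tolerability is also a secondary objective, so exposure after such an event could depend partly on which page a site consulted.

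**Working it through.** No sample size, power or alpha figure is involved. The check sets the two texts side by side, using the protocol's own cut-offs.

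**Can such patients enrol?** Inclusion criteria 14 and 15 admit total bilirubin up to 1.5 x ULN and AST/ALT up to 2.5 x ULN. Section 5.9.2.1 defines Grade 1 as AST or ALT above ULN to 3.0 x ULN, or bilirubin above ULN to 1.5 x ULN. Since 2.5 is below 3.0, an eligible patient can start in Grade 1 on either measure.

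**Which algorithm applies?** Section 5.9.2.1 uses the rise above baseline. With baseline Grade 1:
- Grade 2: 2 - 1 = 1, so the Grade 1 algorithm.
- Grade 3: 3 - 1 = 2, so the Grade 2 algorithm.
- Grade 4: 4 - 1 = 3, so the Grade 3 algorithm.

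The last two match the section's own examples.

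**Comparison for a Grade 1 baseline**

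| Range | Section 5.9.2.1 | Table 6.2.1, Grade 1 block | Agree? |
|---|---|---|---|
| Grade 2: AST/ALT >3 to 5 x ULN or bilirubin >1.5 to 3 x ULN | Grade 1 algorithm: monitoring, no dosing instruction | Continue | Yes |
| Low Grade 3: AST/ALT >5 to 8 x ULN or bilirubin >3 to 5 x ULN | Grade 2 algorithm: ends in resumption | Hold, then resume | Yes in direction |
| High Grade 3: AST/ALT >8 x ULN or bilirubin >5 x ULN, still Grade 3 | Grade 2 algorithm: ends in resumption | Discontinue, no resume step | **No** |
| Grade 4 | Grade 3 algorithm: no resume step | Discontinue | Yes |

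**Is the conflicting band empty?** The documents cite CTCAE v4.0 and do not print the upper limit of Grade 3, so the band's width cannot be stated from them. It is not empty, because the table itself names part of this row High Grade 3.

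**Residual difference in Low Grade 3.** The recovery level for resuming is Grade 1 or baseline in Section 5.9.2.1, and Grade 2 or less, or baseline, in the table. The table may simply be applying the one-grade shift to recovery as well. Section 5.9.2.1 does not say so.

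**The case against.** The strongest reply is that dosing belongs to Section 6.2. Section 5.4.2 refers nivolumab delays and AE management there, Section 6.2 places nivolumab dose management in Table 6.2.1, and the study calendar footnote on dosing sends supportive care to Section 5.9 and dose delay or modification to Section 6.2. The table cites Section 5.9.2.1 for supportive care only, and resuming per protocol can be read as deferring to the table.

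This has weight: a careful reader would probably go to the table. But it is inference. Section 5.9.2.1 names nivolumab resumption itself, Section 6.2 says the algorithms are incorporated into the table (so they ought to agree), and no clause says which prevails. Section 6.2 adds: "The guidance provided in these algorithms should not replace the Investigator's medical judgment but should complement it". That leaves room for judgment but does not tell sites which of two instructions judgment is to complement.

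A reader might infer more than the documents support:
- **Permanent discontinuation.** The hepatic rows do not use that word, though some haematologic rows do. What they lack is a resume step.
- **Conflicting monitoring intervals.** The hepatic rows of Table 6.2.1 give no interval. Every 3 days belongs to the Grade 2 algorithm and every 1-2 days to the Grade 3-4 algorithm, so the two are not rival instructions for one patient.
- **Steroids always delayed 5-7 days.** The Grade 2 algorithm also starts them if values worsen.
- **A conflict for concurrent Grade 2 transaminase and bilirubin rises.** The Grade 1 algorithm has no dosing instruction to oppose the table's discontinue row for concurrent elevation.
- **A hold at baseline in Gilbert's disease.** Entry at "1.5 x ULN OR 3 x ULN for Gilbert's disease" can put bilirubin in the Grade 2 range, which neither block heading covers. That is a missing row. Section 7.1 defines an AE as arising during or after the intervention, so an entry value does not trigger a hold.

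**Conclusion.** The protocol contradicts itself in one band. For a Grade 1-baseline patient with AST/ALT above 8 x ULN or total bilirubin above 5 x ULN that is still Grade 3, Section 5.9.2.1 leads to resuming nivolumab and Table 6.2.1 says discontinue it. The conflict does not extend to all of Grade 3, and Grade 4 is consistent.

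How many patients this would affect is unknown, because the documents give no rate for Grade 1 baselines or for elevations of this size.

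The statistical consequences are limited. The 18-month PFS test is unaffected. A reader might infer that the toxicity monitoring count changes, but under Section 12.3.3 any Grade 3 or higher immune-related AE at least possibly attributed to protocol therapy is unacceptable whether nivolumab is stopped or resumed. Nor does Section 12.3.2 list discontinuation among its toxicity summaries. What remains is inconsistent stopping or re-exposure across sites.

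The conclusion assumes that discontinue, in a row with no resume clause beside a row that has one, means treatment with nivolumab ends. It takes no view on which instruction is clinically right.

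**What to change.** Reconcile the Grade 1-baseline paragraph of Section 5.9.2.1 with the Grade 1-baseline block of Table 6.2.1, so that High Grade 3 carries a single nivolumab instruction in both places. Add one sentence stating which text governs nivolumab dosing if they differ. The clinical content is for the sponsor to decide.

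Two smaller items could be settled in the same edit: the recovery level for resuming in Low Grade 3, and which block applies to patients who enter under the Gilbert's allowance.

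The cost is a wording amendment to one paragraph and one table block, with the IRB review that Section 16.3 requires for any amendment. It adds no visits, tests or patients and leaves the statistical design unchanged.
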